Aim 2: Through an open label treatment study, we will define thiamine deficiency disorders (TDDs) as cases with low or “low normal” thiamine levels and symptoms of TD that improve with thiamine replenishment. Hypothesis 2: The current bioassays of thiamine do not accurately define TDDs and individuals with results the “low normal” range will show symptom improvement with thiamine replacement.

Aim 3: Utilizing a nested case control study design, determine if acute and chronic inflammatory conditions with elevated biomarkers of inflammation increase the risk of developing TDDs. Hypothesis 3: Acute and chronic forms of inflammation cause oxidative stress which increase basal requirements for thiamine as a metabolic cofactor and increase the risk of developing TDDs.

Study Population:

We anticipate 300 patients will be enrolled in this study with an age range of 18 and older. There will be no exclusions due to gender, race, age, or ethnicity. We will endeavor to include women and minorities to the extent possible based on the inpatient population which historically has been predominantly male (95%) and white (90%). All subjects recruited for this study will be Veterans admitted to inpatient units at VA Sierra Nevada Healthcare System hospital (single site recruitment). There will be no minor children participating. The health status will be compromised from mild to severe due to the nature of being hospitalized. We will not include adults unable to consent (those who are cognitively impaired with Impaired Decision-Making Capacity). We will not enroll pregnant women as we do not admit them to the VA hospital due to lack of maternity services.

Inclusion criteria:

- anyone age 18 or older requiring full hospital admission to the medical service.

Exclusion criteria:

- excess alcohol intake as defined by the National Institute of Alcohol Abuse and Alcoholism as more than 14 standard drinks per week for men less than age 65, or more than 7 drinks per week for women or men 65 years of age or older
- unable to consent due to impaired decision making capacity.
- veterans who live more than 75 miles from the study site as that would likely hinder their ability to attend follow up visit 3.
- Veterans who suffer from quadriplegia because they cannot participate in the physical assessments
- Veterans taking thiamine supplements

Vulnerable Populations:

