Measurements: The **primary outcome** of this arm is to describe the prevalence of treatment responsive TDD symptoms in the hospitalized Veteran population. The **secondary outcome** is to explore cut-points of thiamine biomarkers that can be utilized to diagnose TDDs with more sensitivity than current clinical laboratory limits.

Statistical analysis: Descriptive features of treatment responsive TDD patients will include frequencies of symptoms, physical exam findings, and functional disability compared to patients without TDDs. We will describe each case's initial signs and symptoms and improvements. To better define the thiamine levels that differentiate thiamine responsive from thiamine non-responsive symptoms, the levels of thiamine will be compared between groups using Kruskal-Wallis test corrected for multiple comparisons. For the two thiamine biomarkers, the optimal cut-point to distinguish between thiamine responsive and thiamine non-responsive symptoms will be determined by applying the Liu method⁴⁷ to maximize the product of the sensitivity and specificity. Based on the cut-points, thiamine levels will be dichotomized into lower and higher or equal to the cut-point and the area under the receiver-operating curve (AUC), the sensitivity, specificity, positive and negative predictive values, and the likelihood ratio will be computed. These cut-points will be compared to that of the current laboratory reported abnormal cut-points. For this aim the power to identify discriminating cut-points will be dependent up on the prevalence of the treatment responsive disorder and the distribution of thiamine levels. Under conservative assumptions (alpha 0.05, beta 0.80) and a 2 to 1 ratio of negative responders to positive responders at a given thiamine cut-point level, we would need 19 responders and 38 non-responders for a given symptom to estimate an area under the curve (AUC) of 0.725 compared to a null AUC of 0.50. While there is no information to inform the reasonableness of these parameters, we believe we will have reasonable ability to explore thiamine level cut-points for treatment responsive TDD for this exploratory aim.

4.3 Nested case-control study to determine if inflammation is associated with the presence of TD in hospitalized veterans.

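### Aim 2 names sensitivity alone as the yardstick for new thiamine cut-points, and a higher cut-off can meet it even when the biomarker carries no information

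*Combined protocol and SAP*

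**What the plan says.** All of this is in section 15.2 (open label treatment study) unless stated otherwise.

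- **Yardstick.** The secondary outcome is to "explore cut-points of thiamine biomarkers that can be utilized to diagnose TDDs with more sensitivity than current clinical laboratory limits". Specificity is not mentioned in that sentence.
- **Selection.** For each of the two biomarkers the cut-point is chosen by the Liu method, "to maximize the product of the sensitivity and specificity".
- **Direction.** After selection, "thiamine levels will be dichotomized into lower and higher or equal to the cut-point", so a low level is the positive result.
- **Reporting.** An AUC is listed in the same sentence as the dichotomised levels, and "the sensitivity, specificity, positive and negative predictive values, and the likelihood ratio will be computed".
- **Comparison with the laboratory limit.** "These cut-points will be compared to that of the current laboratory reported abnormal cut-points". No metric, interval or condition is given.
- **Separate test of association.** Between responders and non-responders, "the levels of thiamine will be compared between groups using Kruskal-Wallis test corrected for multiple comparisons".
- **Status.** The last sentence of 15.2 calls the aim exploratory.

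Hypothesis 2, under Study Aims/Objectives, begins: "The current bioassays of thiamine do not accurately define TDDs".

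**The concern.** When low is positive, a higher cut-off classifies every patient the lower one did as positive, plus any who fall between the two. Sensitivity stays the same or rises, whether or not the level predicts response to thiamine. The product of sensitivity and specificity tends to be largest near the middle of the distribution when the marker is uninformative, while a laboratory lower limit is usually expected to sit in the lower tail. Together, the selection rule and the stated yardstick tend to produce a more sensitive cut-point from noise.

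At stake is how the result is read. A gain in sensitivity could be offered as support for the first limb of Hypothesis 2 and as grounds for higher diagnostic cut-offs. Cut-points are among the objectives stated in the Background, so the finding is likely to be quoted.

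**Working it through.** **1. The plan's own figure.** Inputs from 15.2: AUC 0.725 against 0.50, two non-responders per responder, alpha 0.05. The text reads "Under conservative assumptions (alpha 0.05, beta 0.80"; I take 0.80 as power. With A the AUC, n₁ responders and n₀ non-responders, the Hanley-McNeil variance is

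Var = [A(1−A) + (n₁−1)(a−A²) + (n₀−1)(b−A²)] / (n₁n₀), where a = A/(2−A) and b = 2A²/(1+A).

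- Null, 19/38: [0.25 + 18(0.0833) + 37(0.0833)]/722 = 0.00669, SE 0.0818.
- A = 0.725: a = 0.5686, b = 0.6094, A² = 0.5256. [0.1994 + 18(0.0430) + 37(0.0838)]/722 = 0.00564, SE 0.0751.
- Two-sided power = Φ[(0.225 − 1.96 × 0.0818)/0.0751] = Φ(0.86) = 80.5%.

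The 19/38 reproduces. It sizes a test of the AUC, not a comparison of two cut-points.

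**2. Where the selected cut-point falls if the marker is uninformative.** Let F be the share of patients below a cut-off. With no relation to response, sensitivity = F and specificity = 1−F, so the product is F(1−F). It is 0.14 × 0.86 = 0.120 at F = 0.14, 0.188 at 0.25, 0.240 at 0.40, and peaks at 0.250 at F = 0.50, the median.

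**3. Where the laboratory limit falls (assumption).** The documents do not give the share of treated Veterans below the limit. Anchors: 14% low in the stroke population cited in the Background; 14/(14+49) = 22% if only low and low-normal patients from that population are analysed; 25%, the expected prevalence in Sample Size and 15.1. I add 40% and 50%, because section 10.3 describes visit 3 as seeing Veterans with low or low-normal levels, which could raise the share.

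**4. Simulation.** Level independent of response (AUC 0.50), 19 responders and 38 non-responders, cut-point maximising in-sample sensitivity × specificity, limit fixed at the assumed percentile, 10,000 trials per setting:

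| Share below laboratory limit | Trials in which the new cut-point is more sensitive |
|---|---|
| 14% | about 99% |
| 22% | 97% |
| 25% | 95% |
| 40% | 70% |
| 50% | 43% |

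With the limit at 14%, mean sensitivity rises from 0.14 to 0.56 and mean specificity falls from 0.86 to 0.56; specificity is lower in about 99% of trials. With a real AUC of 0.725 and 25% below the limit, the new cut-point is more sensitive in 94% of trials, much as under the null.

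**5. Would validation alone cure it?** No. Under the null at 19/38, the selected cut-point still has mean sensitivity 0.48 in new patients, against 0.25 for a limit at the 25th percentile.

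**6. Would the planned AUC protect?** On the undichotomised level, yes. If it is computed after dichotomising at the selected cut-point, as the wording allows, it equals (sensitivity + specificity)/2, and in the null simulation averages (0.56 + 0.56)/2 = 0.56, not 0.50.

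**7. Would comparing the product protect?** No. The in-sample product is the quantity just maximised. A bootstrap that re-selects and scores the cut-point in the same resample gave a 95% interval excluding zero in 90%, 75% and 62% of null trials (limit at 14%, 25% and 40%).

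**The case against.** The strongest reply is that 15.2 contains no decision rule. It says cut-points will be explored and compared, and calls the aim exploratory. The same paragraph plans a multiplicity-corrected Kruskal-Wallis test, specificity, predictive values, a likelihood ratio and an AUC. A reader of the full report would see specificity fall as sensitivity rose. If a gain in sensitivity were read only alongside a rank test at p<0.05, both would occur in about 5% of null trials for limits up to the 25th percentile.

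This stands, and it rules out a stronger reading that a reader might infer: that the plan declares success on sensitivity, so that a worthless and a useful biomarker lead to the same conclusion. The documents set no success criterion, and the planned outputs taken together can tell the two apart. Nor do they propose a formal test of one sensitivity against the other, so no false-positive rate for such a test can be charged to the plan.

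The simulated rates also depend on where the limit lies. Section 10.3 points to a visit 3 group with low or low-normal levels; Study Duration suggests all symptomatic Veterans attend. The share below the limit is therefore undetermined, and rates near 95% or above need it to be about 25% or less.

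What the reply does not remove is that sensitivity is the only property named in the outcome, the comparison with the laboratory limit has no metric, and none of the other outputs is a condition for proposing a cut-point.

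**Conclusion.** The point holds as a minor weakness in a secondary, exploratory outcome. More sensitivity than the laboratory limit is not evidence that a biomarker discriminates or that current assays misclassify patients. With an uninformative marker at 19/38, the planned selection yields a more sensitive cut-point in about 95% to 99% of trials if 14% to 25% of analysed patients lie below the limit, falling to 70% at 40% and 43% at 50%. The gain is guaranteed only in the sense of never being negative when the cut-off is raised; it is strictly positive only if a responder lies between the two cut-offs. The figures assume a fixed limit and a level unrelated to response.

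It would be wrong to infer that Aim 2 as a whole cannot detect a useful marker, since the Kruskal-Wallis test and an AUC on the continuous level can. The second limb of Hypothesis 2, improvement in Veterans with low-normal levels, does not rest on this comparison.

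**What to change.** In 15.2, replace the sensitivity-only yardstick with two statements.

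1. Compute the AUC with its 95% confidence interval on the undichotomised level of each biomarker. Propose a new cut-point only if the lower limit exceeds 0.50; otherwise report the cut-point as descriptive.
2. Report the changes in both sensitivity and specificity against the laboratory limit, with confidence intervals, from optimism-corrected or cross-validated estimates in which the cut-point is selected in the resample and scored on patients not used to select it.

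Add that neither a gain in sensitivity alone nor a gain in the in-sample product will be taken as evidence for Hypothesis 2.

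The cost is a few sentences and a short resampling program in SAS, with no new data. The downside is that no cut-point may be proposed for one or both biomarkers. At 19/38, condition 1 is met in about 3% of trials with an uninformative marker and about 84% with a true AUC of 0.725, so a useful marker would be held back in roughly 15% to 20% of trials, depending on the interval method. That is in line with the 80% power the plan already accepts.

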10.3 Visit 3 – follow-up of symptomatic Veterans after empiric thiamine treatment. All Veterans with low biomarkers OR low normal biomarkers and clinical symptoms of TDDs that were initiated on replacement will be seen at a follow-up visit 3 after two weeks of thiamine replacement. We will repeat the symptom and function survey and repeat the standardized physical assessment. We will categorize changes in symptoms and signs as *no or minimal improvement, or noticeable improvement*. We will re-order thiamine biomarkers to assess for increases in levels. We will recommend continued dosing with thiamine 100 mg daily thereafter for any Veteran with improvement in their symptoms and update their medical record to include thiamine deficiency in their problem list. If a participant failed to complete the 2 weeks of replenishment, we will provide another 2-week course of replenishment and reschedule this visit.

Study Duration/ Study Timeline:

See Table 3. We expect visit 1 will not take substantial time for the Veteran. Visits 2 and 3 will take between 60 and 90 minutes each. For Veterans without symptoms of TD, their participation will be complete after visit 2, before discharge from the hospital. For Veterans with symptoms of TD their participation will be complete after taking thiamine for 2 weeks and attending visit 3. We anticipate the study will end 24 months.

Study Endpoints:

Our primary endpoint will be determining prevalence of TD in our Veteran population. We do not anticipate stopping the study before 300 Veterans are recruited. Thiamine supplements are very safe with few side effects, so we do not anticipate stopping early for safety concerns.

Study Locations:

The study will be conducted at the VA Sierra Nevada Healthcare System Hospital inpatient units at [name]. Follow up visits will occur on the ground floor of the hospital in the research department exam rooms.

International Research:

We will not be conducting this research in international locations.

Participant Compensation:

Those that agree to participate will be compensated \$30 for visits 1 and 2 and \$200 if they attend visit 3 after discharge.

Economic Burden to Participants:

Veterans will not incur any costs because of participating in this study. Those that attend the follow up visit will incur the cost of transportation, but this will be mitigated by the \$200 compensation.

Risk to Participants:

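### Aim 2 chooses each thiamine cut-point and measures its accuracy on the same patients, with no optimism correction and no interval for the cut-point or its accuracy

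*Combined protocol and SAP*

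**What the plan says.** Cut-points are the secondary outcome of Aim 2. Under Measurements in section 15.2 the purpose is to "explore cut-points of thiamine biomarkers that can be utilized to diagnose TDDs with more sensitivity than current clinical laboratory limits". Under Statistical analysis, the Liu method is applied to each of the two biomarkers "to maximize the product of the sensitivity and specificity". Each biomarker is then split at its chosen value and, along with an AUC, "the sensitivity, specificity, positive and negative predictive values, and the likelihood ratio will be computed". The next step is a comparison with existing limits: "These cut-points will be compared to that of the current laboratory reported abnormal cut-points".

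The only sizing statement for this aim is that, with two non-responders per responder, "we would need 19 responders and 38 non-responders for a given symptom to estimate an area under the curve (AUC) of 0.725" against a null of 0.50. The section calls the aim exploratory and admits that nothing informs these parameters.

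Neither section 15.2 nor any other part of the document mentions a validation sample, cross-validation, a bootstrap, or an interval for the cut-points or their accuracy. Recruitment is at a single site and no second cohort is described.

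**The concern.** A cut-point that maximises a criterion in one sample fits that sample's chance features. Accuracy computed at that cut-point in the same sample is biased upwards, and an ordinary interval around it takes no account of the selection.

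The stated purpose is a diagnostic threshold more sensitive than current laboratory limits. Laboratory limits are fixed in advance and carry no such optimism. If accuracy is compared on the same patients, the product of sensitivity and specificity at the Liu cut-point cannot fall below that at the laboratory limit, by construction. If only the cut-point values are compared, a reader needs an interval for the chosen value to judge whether it differs from the limit.

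**Working it through.** **1. The plan's own figure.** Inputs from section 15.2: AUC 0.725 against 0.50, alpha 0.05 (taken as two-sided), power 0.80 (printed as beta), 19 responders and 38 non-responders. The Hanley-McNeil variance is

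V(A) = [A(1−A) + (n1−1)(Q1−A²) + (n0−1)(Q2−A²)] / (n1·n0), with Q1 = A/(2−A) and Q2 = 2A²/(1+A).

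- At A = 0.50: V = (0.25 + 18×0.0833 + 37×0.0833)/722 = 0.00669, SE 0.0818.
- At A = 0.725: Q1 = 0.5686, Q2 = 0.6094, A² = 0.5256. V = (0.1994 + 18×0.0430 + 37×0.0838)/722 = 0.00564, SE 0.0751.
- Power = Φ[(0.225 − 1.96×0.0818)/0.0751] = Φ(0.86) = 80.5%.

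The 19 and 38 reproduce, as the size for testing a full-curve AUC. That calculation does not address the precision of a cut-point or the optimism of accuracy measured at it.

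**2. Size of the optimism.** The document gives no biomarker distribution, so I assumed an equal-variance normal marker, lower in responders by d = √2·Φ⁻¹(0.725) = 0.845 SD. The true best cut then gives sensitivity and specificity of Φ(0.845/2) = 66.4% each. In each of 20,000 simulated samples the cut-point maximising sensitivity × specificity was selected. Accuracy in that sample (apparent) was compared with the accuracy that the same cut-point has in the population (true).

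| Responders / non-responders | Sensitivity, apparent vs true | Specificity, apparent vs true | Excess (points) |
|---|---|---|---|
| 19/38 (plan's per-symptom minimum) | 71.8 vs 64.3% | 70.7 vs 66.9% | 7.5 and 3.8 |
| 38/76 (assumed) | 70.0 vs 65.0% | 69.3 vs 66.8% | 5.0 and 2.5 |
| 63/126 (assumed) | 69.0 vs 65.4% | 68.4 vs 66.7% | 3.6 and 1.8 |
| 28/28 (assumed) | 70.8 vs 65.6% | 71.1 vs 65.8% | 5.2 and 5.3 |
| 38/19 (ratio reversed) | 70.5 vs 66.7% | 72.1 vs 64.5% | 3.8 and 7.6 |

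The 63 borrows the count of TDD cases expected in section 15.1; the 126 keeps the 1:2 ratio. The last two rows show that the split of the excess depends on which group is smaller.

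At 19/38 the median positive likelihood ratio is 2.46 apparent against about 2.0 true, and the positive predictive value 56% against 50%. The sensitivity excess stays at 7 to 8 points for AUC 0.65 to 0.80, and also when the responder SD is 0.67 or 1.5 times the non-responder SD.

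**3. Stability of the cut-point.** The central 95% of selected cut-points lies between these percentiles of the non-responder distribution: 13th to 57th at 19/38, 17th to 52nd at 38/76, and 19th to 49th at 63/126.

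**4. Ordinary intervals.** The plan names none, so a Wilson 95% interval for sensitivity was tried at 19/38. The true value lay below it in 7.9% of runs and above it in 0.3%, against 2.5% each.

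**5. What a bootstrap recovers.** With 200 resamples, re-selecting the cut-point in each, mean sensitivity at 19/38 was 72.2% apparent, 67.3% corrected and 64.5% true; specificity was 70.5%, 68.0% and 66.7%. The correction removes a little under two thirds of the excess, and about the same share at 38/76. The 95% bootstrap interval for the cut-point contained the best cut in 94% of runs at 19/38 and 95% at 38/76.

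**The case against.** The aim is labelled exploratory, the cut-point is a secondary outcome, and the prevalence endpoint does not use it. At 19 responders the standard error of a sensitivity near 64% is √(0.643×0.357/19) = 11 points, more than the 7.5-point excess. Both facts stand and limit the weight of the point. They do not remove it, because sampling error averages out while this excess runs in one direction on average.

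A reader might go further in four ways that the documents do not support.

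- That 19/38 is the planned analysis size, so that 7 to 8 points is the expected bias. It is the minimum for one AUC test on a given symptom. With more patients the excess is about half as large.
- That sensitivity is inherently the most inflated figure. This follows from the plan's assumed 1:2 ratio; with the ratio reversed, specificity takes the larger share.
- That the investigators decided to report no intervals. The text is silent, which is a gap in specification and not a stated choice.
- That the AUC must be the continuous one because the sizing reproduces that way. The reproduction shows how power was computed. The sentence order, with AUC listed after dichotomising, points the other way. The plan only needs to say which it means.

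**Conclusion.** The concern holds. As written, section 15.2 will overstate on average the accuracy of the cut-points it selects, and it gives no means of judging how uncertain those cut-points are. Under an equal-variance normal marker with AUC 0.725 and two non-responders per responder, the excess in sensitivity and specificity is about 7 to 8 and 4 points at 19/38, about 5 and 3 at 38/76, and about 4 and 2 at 63/126. The marker distribution and the two larger sizes are assumptions. Use of the same patients for selection and assessment is inferred, since no other sample exists.

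True accuracy here means accuracy in the patients whose response is assessed. Section 10.3 brings to visit 3 those with low or low-normal biomarkers who began replacement, so the group is itself selected partly on the biomarker. The figures above do not address that.

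This is a cheap improvement of minor to moderate weight. It casts no doubt on the prevalence endpoint or on the 19/38 calculation.

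**What to change.** In section 15.2:

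- Report the apparent sensitivity, specificity, predictive values and likelihood ratio beside values corrected by bootstrap or cross-validation, with the Liu cut-point re-selected in every resample.
- Give resampling-based intervals for each cut-point and for its sensitivity and specificity.
- Use the corrected figures in any accuracy comparison with the laboratory limits, and the cut-point interval when the values themselves are compared.
- State that the results apply to patients whose response was assessed at visit 3, and that resampling does not correct for how that group was selected.
- As wording only, say whether the reported AUC is for the continuous or the dichotomised biomarker, and whether cut-points are found per symptom or pooled. The sizing sentence is per symptom.

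The cost is a few lines of text and a resampling loop in SAS, with no new data and no change to study conduct. The reported accuracy will be a few points lower, there is a little more analysis work, and some optimism will remain.
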